## 7.1 Primary Endpoint

The primary efficacy objective is to evaluate the efficacy of ibrexafungerp in the treatment of severe fungal diseases by a Data Review Committee (DRC) at the primary timepoint for the fungal disease (as defined in [Table 5](#)). The primary efficacy endpoint of the study is the percentage of subjects who achieve Global Response (as defined in [Table 6](#)) at TOC (Day 17) for VVC, CMC (EOT or Day 84), CPA (EOT or Day 90) and ABPA (EOT or Day 90) (whichever comes first) and at EOT for all other diseases, as determined by the DRC. The analysis criteria will be based on EORTC-MSG Consensus Criteria for all diseases except ABPA, CPA and VVC.

Table 6 EORTC-MSG General Criteria for Global Responses to Antifungal Therapy with adaptations a and b

Global Response	Outcome Criteria
Success	Complete Response: Survival within the prespecified period of observation, resolution of all attributable symptoms and signs of disease and radiological abnormalities, and mycological evidence of eradication of disease a For subjects who were enrolled for step-down therapy and who were asymptomatic at baseline: no new symptoms or signs suggestive of disease and no new positive cultures.
	Partial Response: Survival within a prespecified period of observation, improvement in attributable symptoms and signs of disease and radiological abnormalities, and evidence of clearance of cultures or reduction of fungal burden, and no new positive cultures, as assessed by a quantitative and validated laboratory marker
Failure	Stable Response: Survival within a prespecified period of observation and minor or no improvement in fungal disease, but no evidence of progression, as determined on the basis of a composite of clinical, radiological and mycological criteria.
	Progression of Fungal Disease: Evidence of progressive fungal disease based on a composite of clinical, radiological and mycological criteria
	Death: Death during the prespecified period of evaluation, regardless of attribution
bNot Evaluable	Outcome cannot be assessed due to missing data

aDefinition added in Amendment 3 for subjects enrolled for step-down therapy and asymptomatic at baseline. DRC adjudications followed this definition for all subjects, PI adjudication followed this definition for subjects enrolled after Amendment 3.

bCategory added for non-evaluable subjects due to missing data

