- Suspected or confirmed Resistance (includes step-down cases)
- Intolerant
- Toxicities

- Relapse
- Step-down (as determined by PI-assigned enrollment category)
- Other

If Global Response has not been deemed a success or failure, the outcome will be categorized as not evaluable.

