## 7.2 Secondary Endpoints

Secondary endpoints will be presented with 95% CIs for the ITT, Myco-ITT and PP populations using the same approach as for the primary endpoint.

The percentage of subjects surviving at the defined time points will be presented for the ITT, Myco-ITT and PP populations, and will also be presented by disease category. A Kaplan Meier plot will also be produced summarizing the survival curve over time and the median time to death. Survival status information was collected at Day 42 and Day 84 of the study. A subject's date of death will be used to determine their survival status at Day 30. Any subject without a death date and without a record of being contacted on or after Day 30, Day 42, or Day 84 will have a survival status of unknown at those visits. A subject without a reported death will be censored at the point of last time the subject was known to be alive.

The probability of survival will be calculated for the following fungal diseases and timepoints:

• Acute IC with/without Candidemia	Day 30
• Candidemia only	Day 30
• IPA	Day 42

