### 7.2.1 Overall Secondary Endpoints

The overall secondary endpoints listed below apply to all eligible fungal diseases:

- The percentage of subjects who achieve Global Response at additional time points as applicable for each disease, disease category and reason for enrollment ([Table 5](#)), as determined by the DRC and by the Investigator
- The percentage of subjects who achieve Clinical Response by pathogen at time points applicable for each disease, disease category and reason for enrollment ([Table 5](#)), as determined by the DRC and the Investigator
- The percentage of subjects who achieve Mycological Response by pathogen at time points applicable for each disease, disease category and reason for enrollment ([Table 5](#)), as determined by the DRC and the Investigator
- The percentage of subjects who achieve Clinical Response by fungal disease, disease category and reason for enrollment at time points applicable for each disease ([Table 5](#)), as determined by the DRC and the Investigator

- The percentage of subjects who achieve Mycological Response by fungal disease, disease category and reason for enrollment at time points applicable for each disease ([Table 5](#)), as determined by the DRC and the Investigator
- The percentage of subjects with a recurrence of the baseline fungal disease at the 25-Day FU for VVC and at the 6-Week FU for all other diseases as determined by the DRC
- ACM at Day 30 (IC and candidemia) and Day 42 for all diseases
- Time to death from any cause
- Describe ibrexafungerp plasma concentrations

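### Investigator Global Response combines two success definitions for asymptomatic step-down subjects, before and after Amendment 3, and the SAP does not separate them

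*SAP*

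**What the plan says.** SAP 7.1, Table 6, sets out the adapted EORTC-MSG criteria. Footnote a explains one adaptation: "Definition added in Amendment 3 for subjects enrolled for step-down therapy and asymptomatic at baseline". For these subjects Complete Response means "no new symptoms or signs suggestive of disease and no new positive cultures". The same footnote states who used it: "DRC adjudications followed this definition for all subjects, PI adjudication followed this definition for subjects enrolled after Amendment 3".

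Investigator Global Response is a reported endpoint. The first overall secondary endpoint in SAP 7.2.1 is "The percentage of subjects who achieve Global Response at additional time points as applicable for each disease, disease category and reason for enrollment", as judged by both the DRC and the investigator. SAP Table 5 counts EOT among the secondary time points. The analysis rule is in SAP 7.2: "Secondary endpoints will be presented with 95% CIs for the ITT, Myco-ITT and PP populations using the same approach as for the primary endpoint". That approach, in SAP 7.1.1, gives one proportion with a Clopper-Pearson interval per category. One of the enrollment categories is a Step-down row assigned by the investigator. SAP 3 adds an overall rate across all disease categories.

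Neither section splits investigator Global Response by amendment, maps one definition to the other or plans a sensitivity analysis. For investigator mycological response, SAP 7.2.3 does state how results recorded under different protocol versions were mapped to success.

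**The concern.** Which rule an investigator used depends on when the subject was enrolled, whereas the DRC used one rule throughout. The investigator percentage is therefore a mixture of two endpoints, with weights set by enrollment timing. If it is read beside the DRC percentage, part of any difference may come from the definition and not from clinical judgement. The same holds for any apparent change over the enrollment period. The Step-down row is the most exposed, because the affected subjects should be concentrated there.

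SAP 7.2.3 shows that the sponsor recognised this kind of problem for mycological response and dealt with it. For Global Response the footnote discloses the difference, but no analysis rule follows from it.

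**Working it through.** The documents give no figure that depends on this point, so there is nothing to reproduce. The check has two parts.

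**1. One subject under each rule.** Take a step-down subject with no symptoms at baseline and, at EOT, no new symptoms or signs and no new positive culture.

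- Under the Amendment 3 adaptation this is a Complete Response, hence Success.
- Under the general Table 6 rule, Complete Response needs "resolution of all attributable symptoms and signs of disease and radiological abnormalities, and mycological evidence of eradication of disease". Partial Response needs improvement in symptoms, signs and imaging. With nothing to improve, the subject can be placed in Stable Response, described as "minor or no improvement in fungal disease, but no evidence of progression", which Table 6 lists under Failure.

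| Assessor | Enrolled before Amendment 3 | Enrolled after Amendment 3 |
|---|---|---|
| DRC | Success | Success |
| Investigator | can be Failure | Success |

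**2. Scale.** Let s be the share of analysed subjects who are asymptomatic step-down and enrolled before Amendment 3. Let f be the fraction of them whom the investigator scores Failure but who would be Success under the adaptation. Then

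shift in investigator rate = s × f.

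Neither s nor f is in the documents; both are assumptions. Planned N is 220 (SAP 3.1), so s = 5%, 10% and 20% correspond to 11, 22 and 44 subjects. Shift in percentage points:

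| s | f = 25% | f = 50% | f = 80% | f = 100% |
|---|---|---|---|---|
| 5% | 1.25 | 2.5 | 4 | 5 |
| 10% | 2.5 | 5 | 8 | 10 |
| 20% | 5 | 10 | 16 | 20 |

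For comparison, the Clopper-Pearson 95% interval at N = 220 is 48.2% to 61.7% for 121/220 (55%), a half-width of 6.8 points. For 154/220 (70%) it is 63.5% to 76.0%, a half-width of 6.2 points. At f = 80%, a 5% share gives a shift inside that half-width and a 10% share gives one beyond it.

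If results are shown by applicable definition, the two rules are no longer mixed within one rate. If a single rule could be applied to everyone, the shift due to definition would be zero.

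**The case against.** The strongest objection is that nothing in the documents shows how investigators scored these subjects before Amendment 3. With no symptoms present, an investigator could reasonably treat symptom resolution as met and record Complete Response. This stands in part: a reader might infer that identical patients did score differently, and the documents support only that they can. The lenient reading does not close the gap, however. It settles symptoms but not the imaging and mycological eradication that the general rule also requires. Protocol 14.2.2.3 does not make follow-up cultures mandatory for non-bloodstream infections. SAP Table 5 footnote e allows judgement where the criteria do not fit, but only to the DRC.

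Second, the general Table 6 criteria were not the only earlier rule. The amendment history (Protocol 21.1.2 and 21.1.3) shows that the EORTC-MSG table arrived with Amendment 2 and that Amendment 1 had its own definitions. This stands: the Stable Response argument is not shown for the earliest subjects.

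Third, the consequence is limited. The study is exploratory, the primary endpoint is judged by the DRC under one definition, and the SAP plans neither an agreement analysis between investigator and DRC nor an analysis by enrollment period. VVC, CPA and ABPA have their own Global Response definitions. All of this is correct and bounds the point. It does not remove it, because investigator Global Response remains a listed secondary endpoint and Step-down a listed category.

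A reader might also think that a simple recode would suffice, using the investigator clinical category for no attributable signs or symptoms at Screening (SAP 7.2.3). The investigator response guidelines entered with Amendment 2, so the category is not shown to exist for earlier subjects. Overwriting results would also replace what SAP 7.2.3 describes as the investigator's own opinion.

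**Conclusion.** The point holds as a defect in a secondary endpoint. By the SAP's own account, investigators used the step-down rule for only part of the study population, and their Global Response is reported without separating the definitions. The DRC primary endpoint is untouched.

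The size is unknown. Under the stated assumption that 80% of affected subjects are scored differently, the investigator rate is lower by up to 4 points at a 5% share and up to 8 points at a 10% share. Enrollment counts by amendment are not given. The original protocol is dated 30 November 2016 and Amendment 3 is dated 21 November 2022, so a sizeable pre-amendment group is plausible, but that is inference.

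A reader might compute a much larger effect within the Step-down row, for example 0.5 × 0.8 = 40 points if half its subjects were enrolled before the amendment. The documents do not support that figure. It requires every subject in the row to have been asymptomatic at baseline, whereas the adapted rule covers only those who were, and it takes the scoring fraction as given.

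**What to change.** In SAP 7.2, for diseases using the MSG-EORTC criteria:

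- Present investigator Global Response, overall and in the Step-down category, by applicable definition: enrolled before versus after Amendment 3. Note that the earlier group may itself contain more than one rule, because the criteria also changed with Amendment 2.
- State the number of asymptomatic step-down subjects enrolled before Amendment 3. This replaces the assumed share with a count.
- Add a sensitivity analysis that excludes these subjects. Alternatively, apply the Amendment 3 rule only where the recorded components allow it, labelled as derived and not replacing the investigator's assessment.
- Footnote any table that shows investigator and DRC rates side by side, saying that the definitions differ for these subjects.

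The cost is SAP wording and a few extra tables, some with small cell counts. Under SAP 7.1.1, categories with fewer than 5 subjects would have no interval.

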### 7.1.1 Primary Analysis

The primary efficacy analysis will be performed at TOC for VVC (Day 17), CMC (EOT or Day 84), CPA (EOT or Day 90) and ABPA (EOT or Day 90) whichever comes first, and at EOT for all other diseases. For CMC, CPA, and ABPA, if Day 84 or Day 90 is the earlier visit and the Global Response is not evaluable or was not done, and the EOT visit has a Global Response, then the EOT information will be used. The number and percentage of subjects with Successful Global Response as determined by the DRC will be presented separately for each fungal disease, disease category, enrollment category, and pathogen along with a 95% confidence interval (CI) for a single binomial proportion in the ITT and PP populations. The Clopper Pearson method will be used for the confidence interval. CI will not be estimated when the subjects in a particular disease, disease category, enrollment category, or pathogen is less than 5. In addition, the overall response will be presented for all disease categories combined.

The following disease categories and fungal diseases will be used for the analysis.

- Acute invasive candidiasis (IC), including candidemia
  - Acute IC with/without candidemia
  - Candidemia only
- Chronic candidiasis
  - Chronic IC
  - Chronic mucocutaneous candidiasis (CMC)
- Mucocutaneous candidiasis
  - OPC (including oropharyngeal, laryngeal)
  - EC
  - VVC
- Disseminated /invasive dimorphic fungi
- Aspergillus syndromes
  - CPA
  - ABPA
  - IPA
- Other emerging fungi

The following pathogens will be used for the analysis.

- Invasive Candidiasis, including candidemia
  - Albicans
  - Auris
  - Glabrata
  - Krusei
  - Parapsilosis
  - Tropicalis

- Other Candida species
- Mucocutaneous Candidiasis (CMC, OPC, EC, VVC)
  - Albicans
  - Auris
  - Glabrata
  - Krusei
  - Parapsilosis
  - Tropicalis
  - Other Candida species
- Dimorphic fungi
  - Coccidioidomycosis
  - Histoplasmosis
  - Blastomycosis
  - Other Dimorphic fungi species
- Aspergillus Syndromes (CPA, ABPA, IPA)
  - Flavus
  - Fumigatus
  - Nidulans
  - Terreus
  - Other Aspergillus species

Invasive Candidiasis will be grouped according to the following sites of infection:

- Pleural/Pulmonary
- Intraabdominal / Pelvic
- Soft tissue/wound
- Endovascular/endocarditis
- Mediastinitis
- Osteomyelitis
- Native joint
- Prosthetic joint
- Urinary tract
- Other

The following enrollment categories (as determined by DRC unless otherwise stated) will be used for the analysis.

- Refractory
- Suspected or confirmed Resistance (includes step-down cases)
- Intolerant
- Toxicities

- Relapse
- Step-down (as determined by PI-assigned enrollment category)
- Other

If Global Response has not been deemed a success or failure, the outcome will be categorized as not evaluable.

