18.0 Analytical Plan

All statistical analyses will be performed using SAS® version 9.3 or later.

Descriptive statistics (i.e., number of subjects, mean, standard deviation, median, minimum, maximum) will be presented for all continuous variables; number and percentage of subjects will be presented for categorical variables. For parameters measured over time, observed data and changes from Baseline will be described for each time point.

All analyses for ibrexafungerp will present the results by fungal disease, disease category and enrollment category. Overall response will be presented for all disease categories combined.

Unless otherwise stated, data will be analyzed as is with no imputation. Details of the statistical analysis will be provided in a statistical analysis plan, which will be approved prior to final database lock.

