18.3 Interim Analyses and Supplemental Analysis

No interim analyses are planned for this study. If subjects on long-term treatment (CMC, ABPA and CPA) are ongoing at the time of planned data base lock, their data up to TOC visit will be included in the analyses, and data collected after TOC will be reported in a Supplementary Analysis.

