18.4.2 Efficacy Assessments

Response will be assessed by the DRC and by the Investigator. The primary efficacy endpoint of the study is the percentage of subjects who achieve Global Response at TOC for VVC (Day 17), CMC (Day 84), CPA (Day 90), ABPA (Day 90) and at EOT for all other diseases, as determined by the DRC. In cases where EOT for CMC, CPA or ABPA subjects occurs before the planned TOC days, EOT will be TOC assessment. Secondary efficacy endpoints include the percentage of subjects who achieve Global Response, Clinical Response and Mycological Response by pathogen and by disease category (type of fungal disease) at several time points as assessed by the DRC and by the Investigator. The percentage of subjects with a recurrence, ACM and time to death will also be assessed. See [Section 9.0](#) for detailed study endpoints and [Section 14.2](#) for efficacy procedures.

Efficacy outcomes will be based on the definitions captured in [Table 16](#) and [Table 17](#). Criteria for the DRC assessment of response will be further detailed in the DRC Charter. Criteria for the Investigator is outlined in [Section 18.4.5](#).

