**Table 1 Summary of Overall Treatment and Follow-Up Schedule for All Subjects Except VVC Subjects**

Pre-study Activities	Ibrexafungerp Loading Dose	Ibrexafungerp Maintenance Dose	TOC	EOT	6-Week Follow-Up	Additional Follow-Ups
Screening a (Days -1 [-3])	Day 1 a (Baseline) & Day 2	Day 3 to EOT	EOT or Day 84 (CMC) EOT or Day 90 (CPA and ABPA) whichever comes first	Last dose of study drug (up to 180 days from Day 1)	6 weeks ( $\pm 7$ days) after EOT	3 and 6 months after EOT for ABPA subjects only

Abbreviations: ABPA = allergic bronchopulmonary aspergillosis; CMC = chronic mucocutaneous candidiasis; CPA = chronic pulmonary aspergillosis; EOT = end of treatment; TOC = test of cure

a: Screening and Baseline (Day 1) may occur on the same day.

Subjects with VVC will have a Screening visit, a Baseline/Day 1 visit, and scheduled visits on [REDACTED], Day 17 (TOC), 25-day FU (Day 32) and 35-day FU (Day 42). VVC subjects will receive treatment [REDACTED] [REDACTED]. The EOT and 35-Day FU visits may be a phone contact for asymptomatic subjects. A summary of the overall treatment and follow-up schedule for VVC subjects is provided in [Table 2](#).

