## Study Treatments

Eligible subjects (excluding VVC subjects) will receive ibrexafungerp monotherapy given as an initial loading dose of 750 mg BID during the first two days of treatment (Day 1 and Day 2) and then subsequent oral doses of 750 mg QD for up to 180 days depending on fungal disease. Ibrexafungerp given as combination therapy will be required for all subjects with refractory or relapsing invasive pulmonary aspergillosis, mucormycosis and other molds with unpredictable ibrexafungerp activity based on Investigator's judgement and contingent on Sponsor approval. The treatment duration may be extended beyond 180 days, if needed, for certain fungal diseases. Sponsor approval must be obtained for any extension of treatment beyond 180 days. For subjects receiving extended treatment, a 4-week visit schedule may be followed. Subjects who have a recurrence after EOT may also be considered for re enrollment upon discussion with the sponsor. Subjects who are re enrolled will follow the protocol defined visit schedule.

Subjects with VVC will receive oral doses [REDACTED] [REDACTED]. Subjects treated for VVC who have a recurrence after TOC may receive additional cycles of ibrexafungerp treatment, similar to the initial regimen, upon discussion with the sponsor.

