Chronic Pulmonary Aspergillosis (CPA)	TOC (Day 90 or EOT, whichever occurs first) (EOT, Day 90, Day 180, every 3 months while on Tx if beyond Day 180, 6-Week FU)	Global Response = Successful Overall CPA Response , defined as subjects who are judged to have shown improvement of the disease by clinical, radiological and mycological parameters and those that achieved stable disease after entering the study with a rapidly progressing condition.	Global Response (as defined) Clinical Response = defined as improvement or stability in the St. George's Respiratory Questionnaire (SGRQ) score. SGRQ outcomes will be categorized as follows: 
 
• Improvement: Decrease in SGRQ by <math>\geq 4</math> points
 
• Stability: Change in SGRQ between: increase by <math><4</math> to decrease by <math><4</math>
 
• Deterioration: Increase in SGRQ by <math>\geq 4</math> point
 
 Radiological Response will be assessed using chest CT scan and will be categorized as: 
 
• Radiological Improvement: <math>>30\%</math> decrease in volume of fungus ball AND/OR <math>20\%</math> decrease in cavity wall thickening AND/OR <math>20\%</math> improvement in pleural thickening.
 
• Radiological Deterioration: <math>>30\%</math> increase in volume of fungus ball AND/OR <math>20\%</math> increase in cavity wall thickening AND/OR <math>20\%</math> increase in pleural thickening. Subjects with measurements fulfilling any of the criteria for radiological deterioration will be classified as deteriorated, even if they also fulfil a criterion for improvement.
 
• Radiological Stability: No notable change in radiological image.
 
 Mycological Response = reduction in Aspergillus IgG by $\geq 20\%$ AND/OR negative sputum culture for Aspergillus

Fungal disease	Primary time point (Secondary time points)	Primary Outcome Definition	Secondary Outcome Definitions (disease-specific outcome definitions, if not previously defined) a, e

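### SAP 7.1.1 lets a later, unwindowed EOT response replace a missing Day 84/90 response in CMC, CPA and ABPA, contrary to the stated primary time point; with all ITT subjects in the denominator this can raise the success rate but never lower it

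*SAP*

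**What the plan says.** The primary time point for CMC, CPA and ABPA is the earlier of two visits. SAP Table 5 gives it for CPA and ABPA as "TOC (Day 90 or EOT, whichever occurs first"), and for CMC in the same way with Day 84. SAP 7, 7.1 and 7.1.1 repeat it. Protocol 18.4.2 says when EOT may stand in: "In cases where EOT for CMC, CPA or ABPA subjects occurs before the planned TOC days, EOT will be TOC assessment".

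SAP 7.1.1 adds the reverse case. The trigger is "if Day 84 or Day 90 is the earlier visit and the Global Response is not evaluable or was not done"; the consequence is "and the EOT visit has a Global Response, then the EOT information will be used". No limit is set on how late that EOT may be. SAP Table 1 defines EOT as "Last dose of study drug (up to 180 days from Day 1"), and the Study Treatments text adds: "The treatment duration may be extended beyond 180 days, if needed, for certain fungal diseases".

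On missing responses, Protocol 18.4.3 and SAP 7.1.1 class a response that is neither success nor failure as not evaluable (the protocol also says unknown). SAP Table 6 lists Not Evaluable as a third category beside Success and Failure. Neither document says whether these subjects stay in the denominator. ITT is the primary population and contains every enrolled and dosed subject (SAP 3.2 and 7).

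**The concern.** The fallback applies only when Day 84/90 precedes EOT, so it always takes an assessment made after the stated primary time point. A subject whose EOT came first and could not be evaluated gets no second assessment. A subject who continued past Day 84/90 does.

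The result feeds the primary rates by fungal disease, disease category, enrollment category and pathogen, and the combined rate. The study is single-arm and open-label, and Protocol 18.4.3 has these rates assessed against external data. A rule that moves the time point, and can favour the drug under the natural ITT reading, therefore matters to interpretation. The SAP specifies no analysis without it.

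**Working it through.** The plan gives no expected response or missingness rate for these diseases, so there is no figure to reproduce. The check covers timing, direction and an illustration.

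**Timing.** Inputs: planned TOC at Day 84 (CMC) or Day 90 (CPA, ABPA), and planned EOT up to Day 180 (SAP Tables 1 and 5).

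- CMC: 180 − 84 = 96 days late at most.
- CPA, ABPA: 180 − 90 = 90 days late at most.
- With extension beyond Day 180, no upper limit is given.
- For comparison, the Day 84 and Day 90 visits have a window of ±7 days (SAP Table 3; Protocol Table 14).

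**Direction.** Let n be the ITT subjects in a group, x the successes without the rule, m the not-evaluable subjects, k those of the m with a later EOT result, and s the EOT successes among the k.

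- All ITT subjects in the denominator: the rate goes from x/n to (x + s)/n. Since s ≥ 0, it cannot fall. An EOT failure changes nothing; an EOT success adds one.
- Evaluable subjects only: the rate goes from x/(n − m) to (x + s)/(n − m + k). It rises if s/k exceeds x/(n − m) and falls if s/k is smaller.
- PP: membership needs an EOT (TOC) assessment (SAP 3.2). If a substituted EOT meets that condition, an EOT failure can enter the denominator and lower the rate.

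**Illustration (all counts assumed).** n = 30, x = 15, m = 4, k = 4; Clopper-Pearson 95% CIs, as SAP 7.1.1 specifies. The SAP does not pool CMC, CPA and ABPA as one group, so the 30 is only a convenient size.

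| EOT successes among the 4 | All ITT in denominator: without rule → with rule | 95% CI with rule | Evaluable only: without rule → with rule |
|---|---|---|---|
| 0 | 50.0% → 15/30 = 50.0% | 31.3–68.7 | 15/26 = 57.7% → 50.0% |
| 1 | 50.0% → 16/30 = 53.3% | 34.3–71.7 | 57.7% → 53.3% |
| 2 | 50.0% → 17/30 = 56.7% | 37.4–74.5 | 57.7% → 56.7% |
| 3 | 50.0% → 18/30 = 60.0% | 40.6–77.3 | 57.7% → 60.0% |
| 4 | 50.0% → 19/30 = 63.3% | 43.9–80.1 | 57.7% → 63.3% |

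With the full denominator the shift is 0 to 13.3 percentage points, all upward. With the evaluable-only denominator it runs from −7.7 to +5.6 points (50.0 − 57.7; 63.3 − 57.7).

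**The case against.** Several points on the other side are sound.

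- A reader might infer that the rule can only add successes, whatever the analysis. The documents do not support that. They never say that a not-evaluable subject counts as a non-success, and Table 6 separates that category from Failure. The one-way direction depends on keeping all ITT subjects in the denominator.
- A reader might infer that the fallback breaches a ban on imputation. Protocol 18.0 says "Unless otherwise stated, data will be analyzed as is with no imputation" and leaves the details to the SAP, so the SAP may state an exception. That does not reconcile the fallback with the time point that the SAP itself repeats.
- The endpoint was never a single fixed day, because an EOT before Day 84/90 already counts. Variable timing on the early side is part of the design; a later assessment is not.
- A reader might infer that the fallback selects good responders because they stayed on drug. Everyone whose Day 84/90 comes first was still on treatment then, and those who stop later for deterioration also have EOT procedures (Protocol 11.3). EOT failures can be imported too, and the EOT may be only days late. What stands is the unequal second chance.
- A reader might infer that database lock decides who benefits. For CMC, CPA and ABPA subjects still ongoing at lock, Protocol 18.3 says "their data up to TOC visit will be included in the analyses, and data collected after TOC will be reported in a Supplementary Analysis". Such a subject has no EOT to substitute, and nothing shows that anyone is affected.
- SAP Table 5 already lists Day 84 or Day 90, and EOT, as secondary time points. Those results help, but they do not reproduce the unsubstituted primary rate, which also includes subjects whose EOT came first.
- The study is exploratory, with no formal sample size. That limits the consequences but does not settle which time point is primary.

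**Conclusion.** The point holds as a contradiction in the primary analysis. SAP 7.1.1 admits an assessment after the time point that both documents define, with no window, by up to 90 days (CPA, ABPA) or 96 days (CMC) within planned treatment and by more under extension. If all ITT subjects stay in the denominator, the effect on the success rate is zero or upward. With an evaluable-only denominator or in PP, it can go either way. The effect is confined to CMC, CPA and ABPA subjects whose Day 84/90 came before EOT, whose response then is missing or not evaluable, and who have an EOT response. Their number is not given, so the true size is unknown; the 0 to 13.3 points above rest on assumed counts. The change should be made, because these are primary rates set against external data.

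**What to change.** In SAP 7.1.1, replace the fallback for the primary ITT analysis. A CMC, CPA or ABPA subject whose Day 84/90 response is missing or not evaluable remains not evaluable, in the denominator and not counted as a success. State that denominator explicitly. Accept an EOT as the TOC assessment only if it comes first or falls within the existing ±7-day window around Day 84/90.

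Report the EOT-substituted rate as a labelled sensitivity analysis, with the number of subjects substituted and how many days late each EOT was.

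The cost is a short SAP edit and one sensitivity row. The later response is not lost, because EOT is already a secondary time point for all three diseases. The CMC, CPA and ABPA rates, and the combined rates that include them, may be slightly lower.
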